### MANIFEST REFRACTION

Postoperative manifest refractions are to be performed using the M&S System at a distance of 4.0 meters. Manifest refraction is to be performed using the Maximum Plus refraction method as detailed in **Appendix F**. Also refer to **Appendix G**, Refraction Adjustments.

### BEST-CORRECTED DISTANCE VISUAL ACUITY

Monocular visual acuities will be measured using the M&S System at 4 meters (13 feet) under photopic (80-110 cd/m^2) conditions. Instructions for using the M&S System are detailed in **Appendix D**, and for distance visual acuity in **Appendix E**.

### KERATOMETRY

Corneal astigmatism should be determined by biometry keratometric readings. The same method used preoperatively must also be used at the postoperative visit (1-week and 3-month).

### BIOMICROSCOPIC SLIT LAMP EXAM

A biomicroscopic slit lamp exam must be performed at each postoperative visit to determine the presence or absence of any medical or lens findings, complications or adverse events.

Findings of aqueous cells and flare, corneal edema, posterior capsule striae (wrinkles), posterior capsular opacification, and IOL glistenings are to be rated using standardized grading scales of 0 to +4 (0 = none, +4 = severe) during the slit lamp biomicroscopy. The specific grading scales are provided in **Appendix H**.

#### BIOMICROSCOPIC SLIT LAMP PHOTOGRAPHS AND LENS AXIS ORIENTATION

Study subjects are to have their pupils dilated to approximately 6 mm or more at each postoperative visit in order to take slit lamp photographs that capture limbal vessels and iris detail with precise focus, while also capturing the lens fiducial marks with reasonable focus (the camera's focal plane should be anterior to the IOL fiducials; see **Appendix I**).

The lens orientation should also be measured by the investigator, or other study personnel, by rotating the slit lamp beam to match the IOL axis orientation and reading the axis to the nearest degree from the scale (see **Appendix J**).

#### ND:YAG CAPSULOTOMY

If a Nd:YAG capsulotomy is necessary, it is recommended that the procedure be performed at least 1 week prior to a study exam; this is particularly important for the 3-month study visit, as this is the key study exam for evaluation of safety and effectiveness.

#### FUNDUS EXAM

A fundus exam is to be performed at the 3-month visit to evaluate retinal status and fundus visualization. Examinations may be done dilated with ophthalmoscopy.

#### INTRAOCULAR PRESSURE

Intraocular pressure (IOP) is to be measured using the investigator's usual method. It is recommended that the same method be used for all study subjects at the site for the duration of the study.

#### OCULAR SYMPTOMS (NON-DIRECTED; SPONTANEOUS)

Subjective ocular symptoms are to be assessed at each postoperative visit by asking "Are you having any difficulties with your eyes/vision?" Subjects should not be prompted for specific responses; however, if subjects report any issues, they should be recorded, and the level of severity determined (mild, moderate or severe) as appropriate.

#### MEDICATIONS

Postoperative ocular medications should be used as is customary for each investigator and recorded in the source document for each subject, as appropriate. Only medications required for treatment of a serious adverse event (SAE) will be recorded on the case report forms.

#### PATIENT SATISFACTION QUESTIONNAIRE (PSQ)

The 2-item questionnaire will be administered at the 3-month visit to collect information regarding spectacle usage, and subject satisfaction (**Appendix K**). PSQ should be administered only to subjects that undergo bilateral implantation with study lenses.

#### INVESTIGATOR SATISFACTION QUESTIONNAIRE (ISQ)

This 3-item questionnaire is self-administered and should be completed by the PI or sub-PI examining the subject. The purpose of this questionnaire is to collect investigator satisfaction with the clinical outcomes (e.g., rotational stability, uncorrected distance visual acuity) of the eyes implanted with the study lens. At the 1-week and 3-month visits, investigator feedback from the 3-item ISQ will be collected for each implanted eye (**Appendix L**).

#### ADVERSE EVENTS

Subjects should be assessed at each visit for occurrence of and/or change in status of any adverse events, particularly serious and/or device-related adverse events. See **Section 11.0** Adverse Events and **Appendix M** for further information.

#### Secondary Surgical Interventions

Secondary surgical interventions due to refractive error and/or medical complications are serious adverse events. Secondary surgical interventions have become the standard of care in some cases and are considered to be in the subject's best interest. The clinical protocol will allow for secondary surgical interventions in the following categories:

- IOL repositioning due to a significant axis misalignment resulting in a visual outcome that is unsatisfactory, providing the axis misalignment is rotationally correctable.
- IOL exchange due to incorrect spherical power resulting in a significant decrease in uncorrected visual acuity.
- IOL exchange due to surgical or postoperative medical complications or adverse events.

If IOL repositioning procedure is required, the investigator should collect dilated slit lamp photograph showing IOL position prior to reposition.

**NOTE:** *If a toric IOL is repositioned, the subject will continue to be followed through study completion for safety. If a toric IOL is exchanged for a non-toric IOL, the subject should be followed until resolution of the serious adverse event/adverse device effect.*

### **10.8 EXIT OF SUBJECTS**

An Exit CRF will be completed for each subject that completes the study or exits the study before completing all scheduled visits.

It is the responsibility of the investigator to provide complete follow-up data to JJSV for each subject, and every attempt should be made to gather that complete follow-up data for all subjects enrolled, as missing data can have a negative effect on the study results. Patients who would be

traveling, relocating or otherwise unavailable for postoperative follow-up visits should not be enrolled in this clinical study.

A subject will be considered a "screen failure" if he/she does not meet the eligibility criteria, consent is withdrawn prior to surgery, implantation in the first eye is aborted due to a surgical complication, or the subject dies prior to first-eye treatment.

Should a surgical complication occur during the second-eye surgery and result in implantation of a non-study lens, the subject will not be exited from the study; the first eye will continue to be followed per-protocol.

Subjects will be "discontinued" from the study if the subject does not undergo surgery; or if both study lenses are removed; or if the subject dies.

If a subject receives at least one study lens, he/she is to be followed according to the schedule in **Table 2 (Section 10.2)** for visit windows.

Subjects will be considered "lost-to-follow-up" from the study only if irretrievably lost for unavoidable reasons such as: subject moved/unable to locate, subject ill/unable to travel, subject uncooperative/refuses further study participation. In the event of subject relocation, effort must be made by the investigator to secure follow-up information (i.e., slit lamp findings and general visual acuity, etc.) from the subject's new physician.

If a subject is exited early from the study, the investigator must indicate the reason for study exit on the CRF. In the event of a lens removal or other serious adverse event, the subject may be exited from the study; however, effort must be made by the investigator to follow the subject until resolution of the adverse event before exiting the subject from the study.

All study subjects are to be instructed to undergo regular eye examinations at least yearly and also to return to their doctor if any eye complications are experienced.

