## **20. TERMINATION OF THE INVESTIGATION**

JJSV can suspend or terminate the clinical investigation at any time for reasons it determines appropriate. Additionally, the investigator, or JJSV, may stop a subject's participation at any time. However, no suspension of the study would be made to disadvantage the study subjects. Following suspension of the study for any reason, all study subjects who have already received treatment would continue to be followed through completion of the study visit schedule.

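### Section 10.8 permits a whole subject to be exited after one lens removal or another SAE, so eyes that still carry a study lens can miss the 3-month visit

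*Combined protocol and SAP*

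**What the plan says.** **Default.** Section 10.8 asks that "every attempt should be made to gather that complete follow-up data for all subjects enrolled". It adds: "If a subject receives at least one study lens, he/she is to be followed according to the schedule in" Table 2 of Section 10.2, which ends with the 3-month visit. Its list of reasons for discontinuation is no surgery, death, "or if both study lenses are removed".

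**Permission.** Later, Section 10.8 says: "In the event of a lens removal or other serious adverse event, the subject may be exited from the study". The investigator must first make an effort to follow the event to resolution. Section 11.5 likewise asks that a subject leaving because of an SAE be followed until the outcome is known.

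**Re-operation.** The note under Secondary Surgical Interventions in Section 10.7 treats two cases differently. For repositioning: "If a toric IOL is repositioned, the subject will continue to be followed through study completion for safety". For exchange: "If a toric IOL is exchanged for a non-toric IOL, the subject should be followed until resolution of the serious adverse event/adverse device effect". The second says nothing about a fellow study eye.

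**Section 20.** The investigator or the sponsor "may stop a subject's participation at any time". After a suspension of the study, "all study subjects who have already received treatment would continue to be followed through completion of the study visit schedule".

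**The concern.** The permission speaks of a single lens removal, or any other SAE, and releases the subject rather than the eye. Nothing limits it to subjects with no study lens left. Two groups of eyes are exposed:

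- **Case 1:** the unaffected fellow study eye of a bilateral subject whose other eye has had its study lens removed or exchanged for a non-toric lens.
- **Case 2:** an eye that had an SAE without re-operation, together with any fellow study eye, when the event resolves before month 3. Examples are endophthalmitis, retinal detachment or a non-ocular hospitalization; the SAE definition in Section 11.1 does not require a link to the device.

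Sections 6 and 21 make month 3 the key time for acuity, refraction and questionnaires, and Section 10.7 (Nd:YAG capsulotomy) treats it as the main examination for safety and effectiveness. Binocular acuity, the patient questionnaire and the one fundus examination that every treated subject must have after surgery take place only then (Appendix A). With available-data analysis, eyes would be missing because of adverse events, and two sites could handle the same case differently while both follow the protocol.

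**Working it through.** **1. The rules side by side**

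- Non-study lens placed at second-eye surgery (10.6, 10.8): the subject stays and the first eye is followed per protocol.
- Study lens repositioned (10.7): followed to study completion.
- Study lens exchanged for a non-toric lens (10.7): the subject is followed to resolution; the fellow eye is not mentioned.
- Study lens removed from one eye (10.8): the subject may be exited.
- SAE with the lens in place and not repositioned (10.8): the subject may be exited.

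The first and fourth situations can leave the same lens status, one study lens in the first eye, yet retention is required in one and optional in the other.

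**2. Can an event resolve before month 3?**

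Inputs from Section 10.2: second surgery at most 30 days after the first; 3-month visit 60 to 120 days after the second surgery, or after the only surgery.

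- Bilateral, counted from first-eye surgery: earliest 0 + 60 = day 60; latest 30 + 120 = day 150.
- Unilateral: day 60 to day 120.
- Assumed example, a first-eye event that resolves on day 30: the gap to the visit is 60 − 30 = 30 to 150 − 30 = 120 days (bilateral), or 30 to 120 − 30 = 90 days (unilateral).

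Following an event to resolution therefore does not secure the visit. Raised IOP and chronic uveitis can hardly cause early exit, because NOTE 2 in Section 11.1 counts them as serious only at the last visit or beyond 3 months.

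**3. Cost of one exit**

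Inputs from Section 8: 116 bilateral and 76 unilateral subjects.

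- Subjects: 116 + 76 = 192. Eyes: 2 × 116 + 76 = 308.
- Eyes with a fellow study eye: 232/308 = 75.3%.
- Case 1: one fellow eye lost in a bilateral subject, none in a unilateral one; 0.75 on average if every eye is equally likely to be affected.
- Case 2, SAE in one eye: 1 + 0.753 = 1.75 eyes.
- Case 2, non-ocular SAE: 308/192 = 1.60 eyes.
- Each bilateral exit also loses one patient questionnaire and one binocular acuity.

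**4. Scale, for illustration only**

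The plan's one precision figure (Section 21.5) is a half-width of 3.0 points for 200 eyes at 95%. It reproduces: 1.96 × √(0.95 × 0.05/200) = 3.02 points. It belongs to 1-week rotation; the plan sets no 3-month target, so it serves here only as a yardstick.

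Suppose the 200 eyes come from 75 bilateral and 50 unilateral subjects (the 75%/25% target), and assume that 1% to 5% of subjects leave under case 2:

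- 1%: 2 × 0.75 + 0.50 = 2 eyes lost; half-width with 198 eyes 3.04 points.
- 5%: 2 × 3.75 + 2.50 = 10 eyes lost; half-width with 190 eyes 3.10 points.

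Precision hardly moves. What remains is selective loss, whose size and direction the documents do not let us estimate.

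**The case against.** The strongest reply is that Section 10.8 is coherent. Mandatory discontinuation and permitted exit are different things, so scheduled follow-up can be the default and exit after an SAE a discretionary exception. A reader might infer a flat contradiction, with discontinuation allowed only when both lenses are out. The text does not support that: the discontinuation list is not stated to be exclusive, and the section does write an exclusive condition for loss to follow-up. This part of the reply stands.

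The exchange note in Section 10.7 can also be read as a minimum, since it sets follow-up to resolution without mentioning exit. Section 20 is no clear support for retention either. A reader might take it to mean that treated subjects always finish the schedule, but that duty applies after a suspension of the study, and its power to stop an individual subject is unrestricted.

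Oversight exists. The medical monitor reviews SAE reports (Section 16), exit reasons go on the CRF (10.8), accountability data are reported (21.3), and repositioning and exchange rates are an endpoint (6.2). These make the losses visible. None of them requires an eye that still carries a study lens to be seen at month 3, so the gap remains.

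**Conclusion.** The point holds as a cheap improvement. The default and the permission in Section 10.8 pull in different directions, and the follow-to-resolution clauses do not close the gap. An eye still carrying a study lens can be lost to the 3-month data for an event-linked and avoidable reason.

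The effect is probably small. It falls mainly on descriptive 3-month summaries. A reader might infer that the primary result is at risk, but the 1-week endpoint is affected only by exit before that visit, and repositioning, the SAE closest to rotation, already carries follow-up to completion. A reader might also want a loss or bias figure for month 3; without an SAE, removal or exit rate none can be derived. The per-exit costs rest on the planned enrolment mix and, where an eye is affected, on equal risk across eyes. The 1% to 5% exit range and the day-30 resolution are assumptions.

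A lesser wording point: the both-lenses condition does not fit the 76 planned unilateral subjects (76/192 = 39.6%), although the permissive sentence covers them in practice.

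**What to change.** In Section 10.8, replace the permissive sentence with wording such as:

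> While any study lens remains implanted, an SAE or lens removal is not by itself a reason for exit. Eyes with a study lens complete the 3-month visit unless consent is withdrawn, the subject is lost to follow-up or dies, or participation is stopped under Section 20 (reason recorded on the Exit CRF). An eye whose study lens was removed is followed to resolution.

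Then:

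- in the discontinuation list, change the both-lenses condition to: no study lens remains;
- in the Section 10.7 note on exchange for a non-toric lens, refer to the eye instead of the subject;
- align Section 11.5 with the new rule.

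Section 20 stays as it is. The replacement adds no condition to its power to stop an individual subject, so that discretion remains, with the reason on record. The no-imputation rule is also unchanged.

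The cost is a few sentences in three sections and one further scheduled visit, already part of the default schedule, for the few subjects with an SAE. They keep the right to withdraw.

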### **10.9 UNSCHEDULED VISITS**

During the study period, if a non-protocol-required visit is done for the purpose of medically-indicated follow-up for a study eye, data from this visit should be reported using the Unscheduled Visit CRF. The need for unscheduled visits is at the investigator's discretion. Specific examinations to be performed at unscheduled visits are also at the discretion of the investigator (based on the reason for the unscheduled visit) and data are to be recorded in the appropriate section of the CRF.

Data to be collected may include:

- Manifest refraction (using standard Snellen Chart)
- Uncorrected and best-corrected Snellen distance visual acuity
- Intraocular pressure
- Slit lamp examination for medical and/or lens findings

- Slit lamp photographs of IOL position
- Dilated or undilated fundus exam
- Ocular symptoms
- Adverse events
- Medications

If in the opinion of the investigator, IOL misalignment is suspected to be the cause of subjects' visual complaint at an unscheduled visit, the investigator should collect UCDVA, manifest refraction, BCDVA, Keratometry, non-directed visual symptoms, dilated slit lamp photographs (**Appendix I**) and lens axis orientation measurement (**Appendix J**).

***NOTE:** In the opinion of the investigator, if the estimated lens axis orientation remains unchanged since the last study visit, slit lamp photographs need not be repeated.*

Conditions found postoperatively, but previously documented at the preoperative visit, do not trigger an unscheduled visit report. However, if the severity of the condition increases from the preoperative visit, an Unscheduled Visit CRF is needed.

## **10.10 PROTOCOL DEVIATIONS**

Any departure from the protocol procedures represents a protocol deviation. Protocol deviations may be subject-based (e.g., inclusion/exclusion criteria, informed consent deviation, etc.) or procedural-based (e.g., out-of-interval visits, non-compliance with testing procedures, etc.). All protocol deviations will be documented in the Clinical Trial Management System. Any deviation made to protect the life or physical well-being of a subject in an emergency must be reported to JJSV within 5 working days. Protocol deviations will be monitored by the Sponsor, and if the non-compliance is persistent or egregious, Sponsor may take action, including but not limited to termination of the investigator's participation in the study. The investigator is also responsible for informing the reviewing IRB of instances of protocol non-compliance in accordance with the IRB requirements.

## **11. ADVERSE EVENTS AND PRODUCT COMPLAINTS**

### **11.1 ADVERSE EVENT DEFINITIONS**

#### **Adverse Event (AE)**

An adverse event is defined (per ISO 14155) as any untoward medical occurrence, unintended disease or injury, or untoward clinical signs (including abnormal laboratory findings) in subjects, users or other persons, whether related to the study device.

#### **Serious Adverse Event (SAE)**

An adverse event is considered serious (per ISO 14155) if it is an untoward occurrence which may or may not be related to use of the study device that

- is sight- or life-threatening,
- results in death,
- requires inpatient hospitalization or prolongation of hospitalization (a planned hospitalization for a pre-existing condition without a serious deterioration in health is not considered a serious adverse event),
- results in permanent impairment of a body structure or body function,
- necessitates medical or surgical intervention to prevent permanent impairment to a body structure or function, or
- results in fetal distress, fetal death or a congenital abnormality or birth defect

### **Device-Related Adverse Event/Adverse Device Effect (ADE)**

A device-related adverse event is defined as any adverse event that is believed to be definitely, probably, possibly or unlikely to be related to the study device (following the guidelines in Section 11.4, Causal Relationship). A device-related event is also considered an adverse device effect (ADE; following ISO 14155) resulting from the use of the study device that may result from user error, insufficiencies or inadequacies in the instructions for use, deployment, implantation, installation, operation of any malfunction of the device.

### **Anticipated Study-Specific Serious Adverse Events**

The following is a list including, but not limited to, ocular serious adverse events (SAE) that are anticipated and must be reported to JJSV for this study. Any events that are unlikely but anticipated (i.e., endophthalmitis) will be reported to the FDA and other appropriate regulatory agencies. Adverse event definitions in accordance with the American Academy of Ophthalmology Task Force Consensus Statement are included in **Appendix N**.

- Endophthalmitis/intraocular infection
- Hypopyon
- Hyphema
- IOL dislocation
- Cystoid macular edema
- Pupillary block
- Retinal detachment/tear
- Corneal edema
- Chronic anterior uveitis/iritis
- Raised IOP that persists (i.e., is present at the last study visit)

- Toxic anterior segment syndrome
- Visual symptoms requiring secondary surgical intervention (e.g., lens removal)
- Tilt and decentration requiring secondary surgical intervention (e.g., repositioning)
- Residual refractive error resulting in a secondary surgical intervention
- Retained lens material resulting in secondary surgical intervention

**NOTE 1:** Wound “burps” during the first week postoperatively, suture removal, planned blepharoplasty, and Nd:YAG capsulotomy (for PCO) are not considered adverse events for this study.

**NOTE 2:** Corneal edema, and chronic anterior uveitis/iritis will be considered serious according to the guidelines listed in **Appendix N** (i.e., *BCDVA of 20/40 or worse at 1 month or later; and Grade 1+ uveitis/iritis persists for greater than 3 months after surgery*). Raised IOP, according to the guidelines listed in **Appendix N** will be considered serious if present at the last study visit (60-120 days after second eye).

### **Unanticipated Adverse Device Effect (UADE)/Unanticipated Serious Adverse Device Effect (USADE)**

Any UADE (21CFR 812.3(s)) or USADE (ISO 14155) is defined as any serious adverse effect on health or safety or any life-threatening problem or death caused by, or associated with, a device, if that effect, problem, or death was not previously identified in nature, severity, or degree of incidence in the investigational plan (i.e., this protocol), application (including a supplementary plan or application), or risk assessment, or any other unanticipated serious problem associated with a device that relates to the rights, safety, or welfare of subjects.

